### **Study Site:**

This study will be implemented at the Children's Hospital at Montefiore (CHAM). Patients with sickle cell disease will be recruited from the Hematology outpatient clinic and inpatient unit.

### **Population:**

#### Inclusion Criteria:

1. Patients with Hemoglobin SS, SC, SB0thal or SB+thal
2. Patients age 8-21
3. Patients with at least two episodes of primary nocturnal enuresis per week or four episodes over the two weeks prior to enrollment.
4. Patients with secondary enuresis who have been evaluated and cleared by a pediatric urologist as not having other etiologies of enuresis (e.g. overactive detrusor activity, a genitourinary anatomic abnormality)

#### Exclusion Criteria:

1. Patients with developmental delay or neurologic dysfunction secondary to stroke
2. Patients with hypertension or underlying renal disease.
3. Patients with genitourinary anatomic abnormalities. Any prior renal ultrasound showing normal genitourinary anatomy is sufficient to clear a patient for the study.
4. Patients with daytime urinary incontinence
5. Patients with glucosuria on urinalysis.
6. Patients with secondary nocturnal enuresis who have not been evaluated by a pediatric urologist to rule out other etiologies of enuresis.
7. Patients who are pregnant.
8. Patients receiving another medicine for nocturnal enuresis (e.g. imipramine).
9. Patients aged 8-17 who are experiencing pain.

---

 Nevéus T et al, The standardization of terminology of lower urinary tract function in children and adolescents: report from the Standardisation Committee of the International Children's Continence Society. J Urol. 2006;176(1):314. Of note, the term nocturia does not apply to children who awaken for reasons other than a need to void.

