**Table 1**

Age	Enuretic	Non Enuretic	% Enuretic
5-10	8	28	22.2%
11-21	9	18	33.3%
Total	17	46	27 %

Our initial objective was to conduct a randomized placebo controlled double blinded study to assess the efficacy of desmopressin on the rate of nocturnal enuresis in patients with SCD compared to placebo. We also planned to utilize quality of life and fatigue scale questionnaires to evaluate the quality of life in these patients prior to and after treatment. We hypothesized that patients receiving desmopressin would demonstrate fewer episodes of nocturnal enuresis compared to those receiving placebo. Due to low accrual with the study (five participants completed the study and nine participants withdrew from the study), and due to the fact that DDAVP treatment for nocturnal enuresis is already standard of care in a general pediatric population, it was determined beneficial by the investigators to prescribe DDAVP as standard of care and to eliminate the placebo group. The study team will prospectively collect quality of life data for the patients prior to prescribing DDAVP and then one month after initiating treatment with DDAVP. Prior to starting DDAVP an eligibility diary would be filled out on recollection by patient on their enuresis patterns for the past 2 weeks (Appendix 1A). Enuresis diaries would be given to patients and families to track their enuresis but also could be filled out retrospectively with study coordinator either in person or over the phone. We propose to then analyze their laboratory, physical exam, imaging, data prospectively for those patients administered DDAVP as part of their clinical care upon starting the DDAVP. We would prospectively administer surveys on willing participants prior to starting DDAVP and then one month into the intervention. To provide information to the sickle cell research community we propose the following interventions.

The primary objective of this study is:

1. To prospectively assess if the use of desmopressin in patients with sickle cell disease and nocturnal enuresis will decrease the number of nighttime episodes of enuresis by 50% after initiating DDAVP at 0.4 mg nightly dose with dose escalation as clinically appropriate.

Secondary objectives are:

1. To determine if patients with sickle cell disease and nocturnal enuresis receiving desmopressin will have an improved quality of life compared to their baseline.

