2. To determine if patients with sickle cell disease and nocturnal enuresis receiving desmopressin will have less daytime fatigue compared to their baseline data.
3. To determine if the use of desmopressin in patients with nocturnal enuresis improves rates of nocturia, defined as episodes of nighttime awakening to void in children  $\geq 5$  years of age, compared to prior to initiating treatment with DDAVP.

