### **Intervention**

Patients if they meet eligibility criteria will be prescribed DDAVP starting at 0.4 mg every night. Baseline data will be obtained from all patients enrolled in the study using data from 6 months prior to initiating DDAVP. This includes medical history specific to SCD, general medical history (see Appendix 2A), baseline data and labs within the last 6 months (Appendix 2B-D). Renal sonogram will be obtained to assess baseline degree of fibrosis, unless patient has previous normal renal sonogram as part of standard of care.

The day that DDAVP is initiated, patients will complete the Promis Fatigue Scale to measure fatigue as a quality of life measure. We will repeat this questionnaire in a month after starting DDAVP.

Patients will receive 0.4 mg oral desmopressin tablet to be taken at bedtime and will receive similar instructions to take tablet at bedtime with minimal water. They will also be advised not to drink caffeinated beverages four hours before bedtime, not to drink any liquids after taking tablet, and to void right before bedtime. Patients will also be advised to discontinue medication if they develop symptoms of headache, nausea or vomiting, develop an acute illness, or if they are admitted to the hospital and are receiving intravenous fluids.

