Promis Fatigue scale- PROMIS® instruments use modern measurement theory to assess patient-reported health status for physical, mental, and social well-being to reliably and validly measure patient-reported outcomes (PROs) for clinical research and practice. PROMIS instruments measure concepts such as pain, fatigue, physical function, depression, anxiety and social function. The Fatigue scale utilizes a 7-day recall period (items include the phrase "the past 7 days") with five responses. The responses span from never (0) to almost always (4). The Fatigue scale is a 10 item questionnaire whose scores can be approximated if a participant skips a question. A 10-item short form can be scored as long as the participant answered at least 5 items. The Pediatric PROMIS Fatigue scale has been validated for patients aged 8-17 years of age. The surveys will be administered at initiation of medication (week 1) and after completion of 4 weeks of medication. If patients stop and restart the medication the survey will be taken after 4 consecutive weeks of at least 50 % compliance with the medication. This will assess differences in the patients' perception of fatigue after starting the medication. Please see Appendix 4 for Promis Fatigue Scale.

Statistics:

For our study, success in treatment will be defined as a 50% reduction in bedwetting episodes. Our primary endpoint is the improvement in number of wet nights (binary outcome variable) comparing pretreatment and post treatment use of desmopressin. We can expect little or no change in untreated subjects and therefore presume that maximum 10% will improve on their own. Based on the study by Figueroa et al, we can presume that 60% of patients will improve

with desmopressin treatment. In order to detect this 50% difference, we will enroll 50 patients for the study so that the 95% CI for proportion of subjects with improvement after treatment is expected to be (0.46, 0.74) thus will be able to exclude 10% that is expected for untreated subjects. In a secondary analysis, the improvement status will also be correlated to patient characteristics using a logistic regression model. Secondary endpoints are not powered

 Magasi, S. et al. (2011). Content validity of patient reported outcomes: Perspectives from a PROMIS meeting. Quality of Life Research, 25 Aug 2011.

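### The pain exclusion stops at age 17 although enrolment runs to 21, so in 18-21-year-old outpatients a fall in fatigue as pain resolves could be read as a drug effect

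*Combined protocol and SAP*

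**What the plan says.** Inclusion Criteria, item 2, admits "Patients age 8-21". Exclusion Criteria, item 9, removes "Patients aged 8-17 who are experiencing pain". There is no matching rule for ages 18-21, and no reason is given for stopping at 17.

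The Intervention section sets the fatigue baseline without an age limit: "The day that DDAVP is initiated, patients will complete the Promis Fatigue Scale to measure fatigue as a quality of life measure". The scale is repeated about a month later. The Study tools text under Monitoring states that "The Fatigue scale utilizes a 7-day recall period" and that "The Pediatric PROMIS Fatigue scale has been validated for patients aged 8-17 years of age". Secondary objective 2 asks whether patients "will have less daytime fatigue compared to their baseline data", which is a within-patient comparison. The Background explains that the placebo group was dropped, and the Statistics text says that secondary endpoints are not powered.

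**The concern.** Pain at entry keeps a 17-year-old out of the study but not an 18-year-old. If the rule is there to keep pain out of the baseline, the reason holds equally at 18-21, because those patients complete the same scale on the same schedule.

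Pain can plausibly disturb sleep and raise reported fatigue, and the Monitoring section itself names pain as a cause of night-time waking. A patient in pain in the week before starting desmopressin may therefore report high fatigue at baseline. If the pain settles within the month, fatigue may fall whether or not the drug does anything. In a single-arm before-after comparison that fall is counted as improvement on treatment, and no comparison group is available to remove it.

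**Working it through.** **The plan's own figure.** The Statistics text expects a 95% CI of (0.46, 0.74) for the proportion improved, with 50 patients and 60% response. Check: 0.60 ± 1.96 × √(0.60 × 0.40 / 50) = 0.60 ± 0.136 = (0.464, 0.736). It reproduces. It does not depend on the pain rule, so no design figure changes.

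**Does another provision close the gap?**

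- Enrollment: patients enrolled in hospital start only at a visit after discharge. This does not cover outpatients, who are also recruited, and does not require the patient to be free of pain at that visit.
- Monitoring: treatment is held during an acute crisis managed with intravenous fluids. This acts after baseline.
- Monitoring: at the end of the study patients are asked about pain crises or acute chest syndrome during the intervention. This does not record pain at baseline, so it cannot support an adjustment.
- Monitoring: night-time wakings caused by pain are left out of the diary count. This protects nocturia, not fatigue.

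None of these excludes, defers or records baseline pain in an 18-21-year-old outpatient.

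**Possible size.** The documents give neither the age mix nor a rate of pain at entry, so what follows is illustrative.

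1. Share aged 18-21. If ages are spread evenly over 8-21: 4/14 = 28.6%, about 14 of 50. If ages follow the fall in enuresis cited in the Background (36% at 8-10 to 9% at 18-20), take a straight line through 36% at age 9 and 9% at age 19, a slope of −2.7 points per year. Prevalences at 18, 19, 20 and 21 are 11.7, 9.0, 6.3 and 3.6, which sum to 30.6. The sum over ages 8-21 is 14 × (38.7 + 3.6)/2 = 296.1. The share is 30.6/296.1 = 10.3%, about 5 of 50.
2. In pain at baseline: 25-50% (assumed). Low: 0.25 × 5 ≈ 1 patient. High: 0.50 × 14 = 7 patients.
3. Fall in fatigue from resolving pain alone: 10 points in each affected patient (assumed). The scale has 10 items scored 0-4, so on the raw 0-40 total this is one response category on every item. The documents do not say whether raw or converted scores will be compared.
4. Shift in the cohort mean = (number affected / 50) × 10. Low: 1/50 × 10 = 0.2. High: 7/50 × 10 = 1.4.

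Wider assumptions (10-40% aged 18-21, 10-50% of them in pain, a fall of 5-10 points) give 0.10 × 0.10 × 5 = 0.05 to 0.40 × 0.50 × 10 = 2.0 points.

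**The case against.** The strongest reply is that the 8-17 band is exactly the validated range of the pediatric fatigue scale, so item 9 may have been written with that instrument in mind. The match is real, but the documents never make the link. If it is the reason, the gap remains, because the Intervention section gives the scale to all patients and 18-21-year-olds are then scored without the protection given to the younger ones. The match also points to a separate question, the use of the scale outside its validated ages, which a pain item does not answer.

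Second, much is already protected. Patients enrolled in hospital start later, and nocturia counts leave out pain. That stands, and what remains is mainly 18-21-year-old outpatients and one unpowered secondary endpoint.

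Third, the size is one assumption multiplied by another, and it requires the pain to have resolved by the second survey. Persistent pain would produce no such fall. That also stands.

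Fourth, extending the exclusion to all ages is not neutral. It would screen out pain at baseline but not at follow-up, so some patients who start without pain would have it at week 4, biasing the fatigue change against the drug. Accrual was already low: the Background reports five completers and nine withdrawals before the redesign. This is a fair reason not to make a wider exclusion the main remedy. It does not touch the case for recording pain at both surveys.

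**Conclusion.** The point holds as a minor one. The age limit in item 9 is unexplained and does not fit the enrolled age range. It leaves a route by which resolving pain in 18-21-year-olds could be read as reduced fatigue on desmopressin. On the stated assumptions the shift in mean fatigue is about 0.2 to 1.4 points. The true size cannot be derived from the documents.

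A reader might go further and infer two things that the documents do not support.

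- *That the primary endpoint is inflated.* The primary endpoint is a 50% reduction in wet nights. Its baseline is a separate two-week recall: "an eligibility diary would be filled out on recollection by patient on their enuresis patterns for the past 2 weeks". Nothing in the documents says that pain changes wetting.
- *That the planned regression would show a false age effect.* That logistic model relates wet-night improvement to patient characteristics, and no regression of fatigue is planned. A false age effect would again need pain to alter wet nights.

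**What to change.** Add one yes/no item, pain in the past 7 days, to both fatigue surveys for patients of every age. Repeat the fatigue comparison in patients who answer no at both. This matches the scale's recall window and deals with bias in either direction. It does not depend on how item 9 is resolved.

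Reconcile exclusion item 9 with the 8-21 age range, either by applying one pain rule to all ages or by stating why the limit stops at 17.

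Cost: one extra item per survey and a smaller subset in the sensitivity analysis. If the pain rule is widened, a few 18-21-year-olds would start later.

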## **Methods:**

### **Subjects:**

Patients will be recruited for the study in the CHAM outpatient hematology clinic and the inpatient Hematology unit. Medical staff will be educated about the study and designated individuals will obtain consent for administering the PROMIS Fatigue survey prior to initiating medication.

### **Enrollment:**

This study will be a cohort analysis of a standard of care medication administered for nocturnal enuresis. Prior to starting this standard of care medication patients will fill out the PROMIS questionnaire on fatigue. Patients with sickle cell disease who fit the inclusion criteria will be notified about the study when they are seen in hematology clinic, prior to discharge from hospitalization or via phone by study staff. Patients enrolled during hospitalization will not start the trial until a post-hospitalization follow up visit. At this point, the study will be introduced and discussed. Written consent for the survey will be obtained from interested and eligible guardians, or patients, if they are older than 18 years old or an emancipated minor. Patients 7-17 years of age will sign assent. Patients will also be identified for eligibility via the electronic medical record. Patients who fit the inclusion criteria will be called and informed of the medication following a detailed script (see Appendix 6). If they are interested, consent will be obtained at the next outpatient or inpatient visit. Patients and/or guardians will have the option to decline participation or opt out of the study at any point.

### **Intervention**

Patients if they meet eligibility criteria will be prescribed DDAVP starting at 0.4 mg every night. Baseline data will be obtained from all patients enrolled in the study using data from 6 months prior to initiating DDAVP. This includes medical history specific to SCD, general medical history (see Appendix 2A), baseline data and labs within the last 6 months (Appendix 2B-D). Renal sonogram will be obtained to assess baseline degree of fibrosis, unless patient has previous normal renal sonogram as part of standard of care.

The day that DDAVP is initiated, patients will complete the Promis Fatigue Scale to measure fatigue as a quality of life measure. We will repeat this questionnaire in a month after starting DDAVP.

Patients will receive 0.4 mg oral desmopressin tablet to be taken at bedtime and will receive similar instructions to take tablet at bedtime with minimal water. They will also be advised not to drink caffeinated beverages four hours before bedtime, not to drink any liquids after taking tablet, and to void right before bedtime. Patients will also be advised to discontinue medication if they develop symptoms of headache, nausea or vomiting, develop an acute illness, or if they are admitted to the hospital and are receiving intravenous fluids.

### **Monitoring**

Patients will be asked to keep an “enuresis diary” for four weeks (See Appendix 1B). In the diary, patients will record their adherence to the medication, if they had an episode of enuresis, as well as the number of nighttime awakenings specifically secondary to nocturia (and not for

any other reason such as pain or anxiety). All patients will have a follow up call two weeks and four weeks after starting the medication by the study coordinator. Patients will be assessed for improvement in symptoms, medication adherence, and any side effects they are experiencing. Blood pressure, Chem-10, Urine and serum electrolytes and osmolality and urine analysis will be obtained if patient describes any adverse clinical symptoms as would be performed as part of standard of care. Enuresis diaries will be reviewed, and if patients do not have at least a 50% improvement in symptoms they will be advised to make an appointment to investigate if adjustment of the medication based on clinical care would be appropriate. See Appendix 3 for a complete study timeline.

Any patient that has a dose dependent side effect to the medication will have the dose reduced promptly and appropriate clinical management and follow up. If a patient has an acute VOC while taking study medication and is on intravenous fluids, the medicine will be held during the acute event. Individuals will be asked at the end of the study if they had a pain crisis or acute chest syndrome during this intervention.

Be advised that the patients will have up to one year to complete the study. Although the study should only take 4 weeks the patient will not be removed from study unless their participation lasts longer than one year. Children with sickle cell disease frequently have admissions related to their chronic disease that may prevent them from completing study within the 4 week time period. The medication works immediately and a stop in the medication will not cause a decrease in effect of the previous or current doses.

Study tools:

Promis Fatigue scale- PROMIS® instruments use modern measurement theory to assess patient-reported health status for physical, mental, and social well-being to reliably and validly measure patient-reported outcomes (PROs) for clinical research and practice. PROMIS instruments measure concepts such as pain, fatigue, physical function, depression, anxiety and social function. The Fatigue scale utilizes a 7-day recall period (items include the phrase "the past 7 days") with five responses. The responses span from never (0) to almost always (4). The Fatigue scale is a 10 item questionnaire whose scores can be approximated if a participant skips a question. A 10-item short form can be scored as long as the participant answered at least 5 items. The Pediatric PROMIS Fatigue scale has been validated for patients aged 8-17 years of age. The surveys will be administered at initiation of medication (week 1) and after completion of 4 weeks of medication. If patients stop and restart the medication the survey will be taken after 4 consecutive weeks of at least 50 % compliance with the medication. This will assess differences in the patients' perception of fatigue after starting the medication. Please see Appendix 4 for Promis Fatigue Scale.

Statistics:

For our study, success in treatment will be defined as a 50% reduction in bedwetting episodes. Our primary endpoint is the improvement in number of wet nights (binary outcome variable) comparing pretreatment and post treatment use of desmopressin. We can expect little or no change in untreated subjects and therefore presume that maximum 10% will improve on their own. Based on the study by Figueroa et al, we can presume that 60% of patients will improve

with desmopressin treatment. In order to detect this 50% difference, we will enroll 50 patients for the study so that the 95% CI for proportion of subjects with improvement after treatment is expected to be (0.46, 0.74) thus will be able to exclude 10% that is expected for untreated subjects. In a secondary analysis, the improvement status will also be correlated to patient characteristics using a logistic regression model. Secondary endpoints are not powered

 Magasi, S. et al. (2011). Content validity of patient reported outcomes: Perspectives from a PROMIS meeting. Quality of Life Research, 25 Aug 2011.

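### With the placebo arm gone, the only efficacy comparison is against an unsourced 10% for untreated subjects, so a modest response could be credited to desmopressin without support

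*Combined protocol and SAP*

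**What the plan says.** The Background section, after Table 1, explains that low accrual led the investigators "to prescribe DDAVP as standard of care and to eliminate the placebo group". The primary objective is still worded as an effect of the drug: whether "the use of desmopressin in patients with sickle cell disease and nocturnal enuresis will decrease the number of nighttime episodes of enuresis by 50" percent. Enrollment, by contrast, describes the design modestly: "This study will be a cohort analysis of a standard of care medication administered for nocturnal enuresis".

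Statistics defines success as a 50% reduction in bedwetting episodes and sets out the reference: "We can expect little or no change in untreated subjects and therefore presume that maximum 10% will improve on their own". It takes 60% as the expected response, citing an earlier series, and plans 50 patients with an expected 95% CI of (0.46, 0.74), "thus will be able to exclude 10% that is expected for untreated subjects". No other efficacy comparison is given. The 60% carries a citation; the 10% does not.

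Three other places bear on whether 10% is the right reference:

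- **Advice.** Under Intervention, patients given the tablet receive further instructions: "They will also be advised not to drink caffeinated beverages four hours before bedtime". They are also told to avoid liquids after the tablet and to void before bed. Background lists behavior modification among the therapies for enuresis.
- **Selection.** Inclusion criterion 3 is "Patients with at least two episodes of primary nocturnal enuresis per week or four episodes over the two weeks prior to enrollment". Criterion 4, for secondary enuresis, states no frequency.
- **Measurement.** Before treatment, "an eligibility diary would be filled out on recollection by patient on their enuresis patterns for the past 2 weeks". Follow-up is a four-week patient diary (Monitoring), which may be completed retrospectively with the coordinator (Background). Nobody is blinded.

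**The concern.** In a single-arm study the reference rate does the work of the control group. It should be the proportion of these patients who would meet the success definition over the same four weeks, with the same advice, selection and diary, but without the drug. The plan's 10% is for untreated subjects improving on their own, which is a different quantity.

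Advice could raise the no-drug rate. Selecting on a recent count of wet nights, and then using that same fortnight as baseline, invites some regression to the mean. Open-label self-report adds error whose direction is not established, since baseline is recalled and follow-up may be too.

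At stake is what a modest result may be said to show. Followed literally, the plan treats any interval lying above 10% as separating desmopressin from no treatment.

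**Working it through.** **Inputs.** From Statistics: n = 50, expected response 0.60, reference 0.10, 95% CI (taken as two-sided). From Background: the 60% is 6 of 10 patients who elected intranasal desmopressin, without randomization or blinding. No-drug rates above 10% are assumptions; the documents give none.

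**Step 1: reproduce the plan's interval.** Wald: p ± 1.96·√(p(1−p)/n) = 0.60 ± 1.96·√(0.60·0.40/50) = 0.60 ± 0.136 = (0.464, 0.736), which rounds to the stated (0.46, 0.74). For 30/50, Wilson gives (0.462, 0.724) and exact (Clopper-Pearson) gives (0.452, 0.736). The stated figure is correct and matches Wald, although the plan does not name a method.

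**Step 2: the smallest count that excludes a reference.** This is the smallest x of 50 whose lower 95% limit lies above the reference.

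| Reference | Exact | Wilson | Wald |
|---|---|---|---|
| 10% | 10 | 10 | 11 |
| 20% | 17 | 16 | 17 |
| 30% | 23 | 22 | 22 |

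Exact lower limits: 10/50 gives 0.1003, 17/50 gives 0.212, 23/50 gives 0.318. By Wald, 10/50 gives 0.20 − 1.96·√(0.20·0.80/50) = 0.089, which fails, and 11/50 gives 0.105, which passes. An observed response of 20–22% is therefore enough under the plan.

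**Step 3: how often an inert drug would pass.** If the drug adds nothing and the no-drug rate is r, the number improved is X ~ Binomial(50, r).

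| r | P(X ≥ 11), Wald | P(X ≥ 10), exact or Wilson |
|---|---|---|
| 10% (plan) | 0.009 | 0.025 |
| 15% (assumed) | 0.120 | 0.209 |
| 20% (assumed) | 0.416 | 0.556 |
| 30% (assumed) | 0.921 | 0.960 |

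The comparison is sound if 10% is right, and deteriorates quickly if the true figure is only somewhat higher.

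**Step 4: does this threaten the planned result?** At 30/50 the lower limit is 0.45 to 0.46, so 20% and 30% are excluded too. At a true response of 60%, the chance of reaching 23 of 50 is 0.984 and of reaching 17 of 50 is 0.9999.

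**Step 5: could the response be lower?** The exact 95% CI for 6/10 is 0.26 to 0.88, so a response well below 60% is compatible with the planning source. The chance of a result that excludes 10% but not a higher assumed reference (exact CI) is:

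| True response | 10–16 of 50 (20% not excluded) | 10–22 of 50 (30% not excluded) |
|---|---|---|
| 60% | 0.01% | 2% |
| 50% | 0.8% | 24% |
| 45% | 4% | 50% |
| 40% | 16% | 77% |

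The size of the ambiguous zone depends heavily on which assumed reference is used.

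**The case against.** The strongest reply is that the plan does have a rule and that nothing in it is shown to be false. That is largely right. Four stronger readings are tempting, and the documents do not support them.

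- **That 10% is wrong.** Some of the text fits little change over four weeks. Enuresis prevalence falls only over about a decade (36% at 8–10 years to 9% at 18–20). Two alarm users had no improvement after three and four months. Background reports the view that the renal defect is irreversible and progressive. In Table 1 enuresis is no rarer at 11–21 years (33.3%) than at 5–10 (22.2%), in a small sample. None of this measures a four-week responder rate under the same advice and diary, so 10% is unsupported rather than refuted.
- **That there is no decision rule.** Success definition, interval and comparison are all stated, and passing counts can be computed from them. The rule is weak for attribution; it is not absent.
- **That the sample size fails.** It does not: the planned result clears 30%.
- **That an ambiguous result is likely.** The 24–77% figures for true responses of 50% down to 40% come almost entirely from choosing 30% as the second reference. With 20% they are 0.8–16%.

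Two further points stand. The fluid advice is also a stated safety measure, so it is arguably part of treatment as prescribed, and the plan does not say whether patients had heard such advice before. Background also cites a placebo-controlled benefit of 1.34 nights per week in the general pediatric population, so belief in a drug effect need not rest on this cohort alone. The same section, however, doubts whether the drug works through the renal defect of sickle cell disease.

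**Conclusion.** The point holds for modest results only. Excluding an unsourced 10% is the sole efficacy comparison, and that 10% describes a condition that differs from participants' own no-drug state in advice, selection and measurement. A result of 10 or 11 of 50 would satisfy the plan, and an inert drug would produce such a result or better 12–21% of the time at a no-drug rate of 15% and 42–56% at 20%. Both rates are assumptions. The documents give no distribution of wet nights and no effect of advice from which to estimate the true figure.

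If about 60% improve, the choice between 10%, 20% and 30% makes no difference. The result would still be uncontrolled, but not fragile to this number. The absence of a source and of a control is certain; how much it matters depends on the unknown no-drug rate and on the response observed. It is a cheap improvement that should be settled before the data are seen.

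**What to change.** In Statistics, keep N at 50 and make four changes:

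1. Give a source for the 10%, or label it an assumption.
2. State that the proportion improved will be reported with an exact (Clopper-Pearson) 95% CI. Naming the method matters slightly, because thresholds differ by one patient between methods.
3. Add a sensitivity display showing whether the interval also excludes assumed no-drug rates of 20% and 30% (at least 17 and 23 of 50), marked as illustrative and not as pass/fail tiers.
4. State the limit on the conclusion. Suggested wording: *The no-drug improvement rate under the same advice and diary is not known. The result will be described as uncontrolled before/after improvement under desmopressin plus advice; exclusion of 10% alone will not be reported as evidence of a drug effect.*

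This needs no extra patients or visits and no change in clinical care. The cost is a more cautious statement if response is modest. With complete follow-up, the chance that the exact interval also excludes 30% is 98% at a true response of 60%, 76% at 50% and 50% at 45%. For 20% the chances are above 99.9%, 99% and 96%. No fixed reference replaces a control group, so the limit on the conclusion applies even when 30% is excluded. Handling of patients without follow-up data is a separate question and is not part of this change.
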